6.1.2. Adverse Events of Clinical Interest

6.1.2.1. Infusion Related Reactions

The incidence of infusion related reactions (IRRs), as flagged on the eCRF, will be presented by SOC, PT, and toxicity grade 3/4. Treatment modifications due to IRRs will also be summarized.

A listing of all IRRs will be provided.

6.1.2.2. Dose Limiting Toxicity

The dose limiting toxicity observed during the safety run-in phase will be listed.

6.1.2.3. Immune-mediated Adverse Event

The incidence of immune-mediated adverse event, as flagged on the eCRF, will be presented by SOC, PT, and toxicity grade 3/4. Treatment modifications due to these events will also be summarized.

A listing of all immune-mediated AEs will be provided.

6.2. Deaths

Number of subjects who died during the study and the primary cause of death will be summarized. In addition, all deaths within 30 days of last infusion will be summarized.

A listing will be generated for all subjects who died during the study.

6.3. Clinical Laboratory Tests

Descriptive statistics for values and changes from baseline over time for these laboratory parameters will be provided. In addition, shifts from baseline toxicity grade to worst toxicity grade during treatment will be generated.

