– Prothrombin time/International Normalized Ratio	– Activated partial thromboplastin time
Chemistry	
– Sodium	– Total bilirubin ^b
– Potassium	– Alkaline phosphatase
– Creatinine	– Lactic acid dehydrogenase (LDH)
– Aspartate aminotransferase (AST)	– Calcium ^a
– Alanine aminotransferase (ALT)	– Amylase, lipase
Urinalysis^a	
Standard Urine Dipstick	
Other Tests	
Thyroid panel ^a	Serology (hepatitis B, hepatitis C) and HCV Viral Load: ^a
– Thyroid stimulating hormone (TSH)	– Hepatitis B: HBsAg, anti-HBc
– Triiodothyronine (T3; total or free)	– Hepatitis C: anti-HCV; HCV RNA PCR, if necessary
– Free thyroxine (T4)	
Pregnancy Test (for women of childbearing potential only)	
– serum (<5 IU/mL) β -hCG at Screening; serum or urine thereafter as clinically indicated	

a. Not performed for subjects who crossover from Arm A to Arm B, except as clinically indicated.

b. Direct bilirubin if Gilbert disease.

Indirect Antiglobulin Test (IAT) results

This test no longer needs to be performed since daratumumab treatment is discontinued.

Blood Type, Rh, and Indirect Antiglobulin Test (IAT) should be done before the first dose of daratumumab. Subject red blood cell (RBC) phenotyping (standard or extended) is an alternative option to the IAT test, if locally required. Either method must be completed prior to first daratumumab infusion.

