11.8. Safety Analyses

Adverse Events

The verbatim terms used in the CRF by investigators to identify adverse events will be coded using the Medical Dictionary for Regulatory Activities (MedDRA). Treatment-emergent adverse events are AEs with onset during the treatment phase or that are a consequence of a pre-existing condition that has worsened since baseline. All reported adverse events will be included in the analysis. For each adverse event, the percentage of subjects who experience at least 1 occurrence of the given event will be summarized by treatment group. In addition, comparisons between treatment groups will be provided if appropriate.

Summaries, listings, datasets, or subject narratives may be provided, as appropriate, for those subjects who die, who discontinue treatment due to an adverse event, or who experience a severe or a serious adverse event.

Clinical Laboratory Tests

Laboratory data will be summarized by type of laboratory test. Reference ranges and markedly abnormal results (specified in the Statistical Analysis Plan) will be used in the summary of laboratory data. Descriptive statistics will be calculated for each laboratory analyte at baseline and for observed values and changes from baseline at each scheduled timepoint. Changes from baseline results will be presented in pre- versus posttreatment cross-tabulations (with classes for below, within, and above normal ranges). A listing of subjects with any laboratory results outside the reference ranges will be provided. A listing of subjects with any markedly abnormal laboratory results will also be provided.

Parameters with predefined NCI-CTCAE toxicity grades will be summarized. Change from baseline to the worst adverse event grade experienced by the subject during the study will be provided as shift tables.

Electrocardiogram

Electrocardiogram data will be summarized based on categories of normal, abnormal either clinically significant or not clinically significant and listed.

Vital Signs

Descriptive statistics of temperature, pulse/heart rate, and blood pressure (systolic and diastolic) values and changes from baseline will be summarized at each scheduled timepoint. The percentage of subjects with values beyond clinically important limits will be summarized.

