2.1. Baseline, Relative Day

Baseline value is defined as the last non-missing value obtained prior to the first dosing date/time of study medication.

Day 1 is the first dosing date of study medication. Study Day is defined as assessment date – first dose date + 1 for any assessment done on or after first dose date; otherwise, study day is defined as assessment date – first dose date.

Unless specified otherwise, data to be analyzed or presented over time will be presented by visit and time point (as appropriate) that are recorded in the eCRF.

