2.6. Other General Definitions

2.6.1. Treatment Groups

The treatment groups are atezolizumab (Arm A) and atezolizumab + daratumumab (Arm B).

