2.6.10. Treatment Emergent Adverse Events

Treatment emergent adverse events (TEAEs) are defined as any AE with onset date and time on or after that of the first dose through 30 days after the last study drug administration, or the day prior to start of subsequent therapy, whichever is earlier; or any AE that is considered related to (very likely, probably, or possibly related) study medication regardless of the start date of the event. AEs with missing or partial onset date and time will be considered as treatment-emergent unless the onset date and time of an AE can be determined as earlier than that of the first dose, or later than 30 days after last study drug administration.

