6. SAFETY

The safety profiles of Daratumumab will be evaluated by the incidence of adverse events (AEs), death, laboratory results, vital signs, physical examination findings, ECG results, and ECOG score overtime.

Safety summaries will be provided by treatment received. The severity of AEs and the toxicity of laboratory parameters will be assessed using NCI CTC version 4.03. Adverse events are coded using latest version of MedDRA coding dictionary.

For cross-over subjects, safety data after initiation of cross-over treatment may be summarized separately, as appropriate.

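### Separating post-crossover safety data is optional in the SAP, so toxicity arising on the combination can be counted against atezolizumab monotherapy

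*SAP*

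**What the plan says.** The rules that bear on this are spread over several sections.

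- **Laboratory window.** SAP 6.3: "shifts from baseline toxicity grade to worst toxicity grade during treatment will be generated". Protocol 11.8 describes the same table with a wider window: "Change from baseline to the worst adverse event grade experienced by the subject during the study will be provided as shift tables".
- **Adverse event window.** SAP 2.6.10 counts events from the first dose "through 30 days after the last study drug administration, or the day prior to start of subsequent therapy, whichever is earlier". It also counts any event judged related to study medication, whatever its start date.
- **Baseline.** SAP 2.1: "Baseline value is defined as the last non-missing value obtained prior to the first dosing date/time of study medication". No second baseline is defined at crossover.
- **Grouping.** SAP 6: "Safety summaries will be provided by treatment received". SAP 2.6.1 defines two treatment groups, one per randomized arm, and no crossover group.
- **Crossover.** SAP 6: "For cross-over subjects, safety data after initiation of cross-over treatment may be summarized separately, as appropriate".

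Crossover did take place. Protocol 1.4 and 3.2 refer to Arm A subjects who had moved to the combination by the time daratumumab was stopped. Neither section says how many.

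**The concern.** Assessing the safety of the combination is the first secondary objective (SAP 1.1). The between-arm comparison informs that assessment only if the Arm A column reflects atezolizumab alone. An Arm A subject who crosses over is exposed to daratumumab, and nothing in the stated windows closes the Arm A record at that point.

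The events at issue matter. Protocol 1.3.1 lists anemia, neutropenia and thrombocytopenia among the most frequent events on daratumumab in myeloma, and Protocol 9.7 names hemolysis and thrombocytopenia for close monitoring. If such events after crossover fall in the Arm A column, the monotherapy rate rises and the difference between arms shrinks, which makes the combination look safer by comparison.

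**Working it through.** The plan states no figure on this point, so there is none to reproduce. The check is a reading of the rules together, followed by simple arithmetic on size.

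**1. Are the relevant tests still done after crossover?** Yes. Footnote a to the laboratory table in Protocol 9.7 reads "Not performed for subjects who crossover from Arm A to Arm B, except as clinically indicated". It is attached to coagulation, calcium, urinalysis, the thyroid panel and serology. Hematology and the rest of the chemistry panel carry no such waiver.

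**2. Where would a low count after crossover have arisen?** Crossover criterion 5X (Protocol 4.3.1) requires neutrophils above 1.5 × 10⁹/L, platelets above 100 × 10⁹/L and hemoglobin above 9 g/dL within 28 days before the first crossover dose. These are the study-entry limits in Protocol 4.1. A subject who meets them and later has a severe cytopenia most likely developed it on the combination.

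**3. Follow one such subject through the rules.**
- Window: SAP 6.3 takes a single worst grade on treatment, and crossover treatment is study treatment. Under Protocol 11.8 the window is the whole study. Either way the post-crossover grade qualifies.
- Column: grouping by treatment received does not settle it, because the subject received both treatments in sequence and there are only two groups.
- Separation: a separate summary is permitted, but producing one does not remove the value from the Arm A table.
- Visit labels do not help here. By-visit summaries follow the visits on the case report form (SAP 2.1), and crossover cycles have their own labels (Cycle 1X and 3X in Protocol 9.6.1). A worst-grade table collapses visits, so that separation is lost.

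**4. If the separate table is made, is its baseline right?** Not under SAP 2.1 as written. The only baseline is before monotherapy. Lymphocytes, sodium, creatinine, amylase and lipase have no threshold in criterion 5X, so a grade that had already worsened on atezolizumab alone could appear as a shift on the combination.

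**5. Size per subject.** Protocol 1.4 gives 44 subjects per arm at the third data review. Taking all 44 in Arm A as treated, each crossover subject whose first event of a given kind comes after crossover adds 1/44 = 0.0227, or 2.3 percentage points, to the Arm A rate.

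**6. Total size, as an illustration only.** Let c be the share of Arm A crossing over, p the event rate on monotherapy, and q the rate after crossover among those with no earlier event. Assume crossing over is unrelated to having had an earlier event. Without a cut-off the Arm A rate is p + c(1 − p)q; with one it is p. The documents give none of c, p or q. Over assumed ranges of 10–50%, 10–20% and 10–30%:

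| c | p | q | Rise in Arm A rate, c(1 − p)q |
|---|---|---|---|
| 10% | 20% | 10% | 0.10 × 0.80 × 0.10 = 0.8 points |
| 25% | 10% | 20% | 0.25 × 0.90 × 0.20 = 4.5 points |
| 50% | 10% | 30% | 0.50 × 0.90 × 0.30 = 13.5 points |

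If the Arm B rate is the higher one and is left unchanged, the difference narrows by the same amount.

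**The case against.** The SAP is not silent. The opening of Section 6 governs the laboratory and adverse event tables, groups them by treatment received, and names the start of crossover treatment as the split. The protocol also supports a boundary: Section 3.1 ends assigned Arm A treatment at crossover, Section 4.3 requires the End of Treatment Visit before crossover screening, and the abbreviations list has a separate end of treatment for crossover. A sensible programmer might well cut there. Under a treatment-received rule, Arm A is also the least natural home for a value measured on daratumumab.

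All of that stands, and it rules out two stronger readings: that the plan ignores crossover, and that post-crossover data will be tabulated under Arm A. They may equally go to the combination column or to a separate table. In the combination column the distortion differs, because shifts would be measured from a baseline taken before monotherapy.

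For adverse events, it could be argued that crossover is itself a subsequent therapy and so closes the window. The protocol does not use the term that way. Section 4.3.2 makes subsequent anti-cancer therapy a reason to refuse crossover, and refers to the crossover drugs as study drug.

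There are other safeguards. Clinically relevant laboratory changes are recorded as adverse events (Protocol 9.7), all treatment-emergent events are listed (SAP 6.1.1), and Protocol 11.8 requires listings of abnormal results. The shift table is descriptive, with no decision rule attached. The safety run-in set gives a view of the combination that crossover does not touch. These limit the harm but do not correct the Arm A rate. The data presentation specifications were not available. SAP 2.5 sends imputation rules there, and whether they cover crossover windows is unknown.

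**Conclusion.** The concern holds as a gap in the rules for all safety tables, most visible in the worst-grade laboratory table. Separation at crossover is named but optional. The stated windows do not stop there, the only baseline precedes monotherapy, and nothing says that later data leave the Arm A tables. Applied literally, these rules let toxicity from the combination period count against monotherapy.

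The effect is up to 2.3 percentage points on an Arm A rate per affected subject, with 44 as the denominator. The total is unknown because the number of crossovers is not given; the range of 0.8 to 13.5 points above rests wholly on assumed inputs. With few crossovers the effect is small.

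A reader might go further and infer that the absence of unexpected toxicity imbalances reported in Protocol 1.4 was produced by this gap. The documents do not support that: they do not say how crossover was handled in the tables the committee saw. The plan should be corrected on this point, but the gap does not show that any reported result is wrong.

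**What to change.** In SAP 6, change *may* to *will* in the crossover sentence and add wording such as: for Arm A subjects who cross over, Arm A safety tables use only data before the first crossover dose; data from that dose onward appear in a separate crossover summary, in which the laboratory baseline is the last value before the first crossover dose.

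Refer to this rule in SAP 6.3 for the worst-grade shifts, and in SAP 2.6.10 for both the time window and the clause on related events. Add the crossover baseline to SAP 2.1. The cut agrees with Protocol 3.1 and 4.3.

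The cost is a few SAP sentences, one baseline flag and one additional crossover summary. It uses dosing dates, laboratory values and adverse event records already collected.

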6.4. Vital Signs and Physical Examination Findings

Descriptive statistics will be provided for values and changes from baseline over time for vital signs.

6.5. Electrocardiogram

Frequencies of overall interpretation of ECG results (normal, abnormal and clinically significant, abnormal and not clinically significant) over time will be provided.

6.6. Other Safety Parameters

6.6.1. ECOG Performance Status

Frequencies of ECOG performance status (0, 1, 2, >2) over time will be summarized.

7. PHARMACOKINETICS/IMMUNOGENICITY/PHARMACODYNAMICS

For cross-over subjects, pharmacokinetics/immunogenicity/pharmacodynamics data after initiation of cross-over treatment may be summarized separately, as appropriate.

7.1. Pharmacokinetics

Pharmacokinetic analyses will be performed on the pharmacokinetic-evaluable population. All serum concentrations below the lowest quantifiable concentration or missing data will be labeled as such in the concentration data presentation. Concentrations below the lowest quantifiable concentration will be treated as zero in the summary statistics. All subjects and samples excluded from the analysis will be clearly documented in the study report.

Descriptive statistics (e.g., number of observations, mean, standard deviation, median, and range) will be used to summarize daratumumab and atezolizumab serum concentrations at each sampling time point. Line plot of mean (\pm SD) daratumumab and atezolizumab serum peak and trough concentrations over time will be provided. In addition, coefficient variation and geometric mean will be provided in the pharmacokinetic concentration summary.

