e. A serum sample for selected cytokines should be drawn within 6 hours of suspected cytokine-release syndrome, and submitted to the central laboratory.

The Sponsor will closely monitor and evaluate the collection of cytokine samples and will notify the participating centers of any change to the collection requirements.

The serum sample for cytokines is also specified in Section 6.2.1.9.

Time and Events schedules for pharmacokinetic and immunogenicity assessments (Table 3 and Table 6[new]); 9.3.2 Analytical Procedures	
Cycle 1 Day 1 predose pharmacokinetic sample for atezolizumab will be for all arms (Safety Run-in, Arm A, Arm B, and crossover). The Cycle 1 Day 2 predose sample is removed.
 
The every 8 Cycles after Cycle 8 (Day 1) samples are removed and replaced with Cycle 12 and Cycle 16 samples.
 
Revised footnote a: Daratumumab should always be administered prior to atezolizumab. In subjects receiving both agents, predose PK and immunogenicity samples for daratumumab and atezolizumab should always be obtained up to 2 hours before the start of the daratumumab infusion, even in Cycle 1 when atezolizumab is administered one day later on Day 2. End of infusion samples are to be taken within 2 hours after the end of the infusion of the respective drug.
 
Predose sample to be taken up to 2 hours before the start of the infusion; end of infusion sample to be taken within 2 hours after the end of the infusion.
 
New footnote b (Table 3): If an Arm A subject crosses over to combination treatment, follow-up samples will not be obtained until after all dosing is complete (Table 6).
 
In Section 9.3.2, this sentence is revised: Serum samples will be analyzed to determine concentrations of daratumumab, concentrations of atezolizumab, or the generation of antibodies to daratumumab or atezolizumab using validated immunoassay methods by or under the supervision of the Sponsor's bio-analytical facility.

Time and Events schedules for biomarker assessments (Table 2 and new Table 5); Time and Events schedules for pharmacokinetic and immunogenicity assessments (Table 3, footnote a, and new Table 6)	It specified that if a dose delay occurs, then samples should be taken on the actual day of drug administration, not on the originally scheduled administration day.
Title page; 1 Introduction	Current approvals for atezolizumab and daratumumab are updated.

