1.3.1. Daratumumab IV

Human Pharmacokinetics and Immunogenicity

Daratumumab clearance decreases with increasing dose and repeated dosing, indicating target-mediated pharmacokinetics. Following the approved multiple myeloma schedule and dose of 16 mg/kg, the mean serum maximum observed concentration (C_{max}) at the end of 8 weeks of weekly dosing was 915 $\mu\text{g/mL}$, approximately 2.9-fold higher than following the first infusion. The mean predose (trough) serum concentration at the end of weekly dosing was 573 $\mu\text{g/mL}$. Based on the population pharmacokinetic (PK) analysis, daratumumab steady state is achieved approximately 5 months into the every-4-week dosing period (by the 21st infusion), and the mean ratio of C_{max} at steady-state to C_{max} after the first dose was 1.6. The mean estimated terminal half-life associated with linear clearance was approximately 18 days.

Of the 199 total subjects in Studies GEN501 and MMY2002 that were evaluable for immunogenicity, none were positive for anti-daratumumab antibodies.

Efficacy/Safety Studies

The US FDA and European Commission (EC) have approved daratumumab for the treatment of patients with multiple myeloma who have received at least 3 prior lines of therapy including a PI and an IMiD or who are double-refractory to a PI and an IMiD. These approvals were based on data from the pivotal study MMY2002 and key supportive study GEN501.

Integration of data from Study MMY2002 and Part 2 of Study GEN501 resulted in an ORR of 31% with duration of response of 7.6 months. Median time to first response is slightly less than 1 month, corresponding to the first disease assessment. The response at the dose of 16 mg/kg was consistent across all subgroups, regardless of the number of prior lines of therapy, refractory status, or geographic region. The rate of very good partial response (VGPR) or better induced by single-agent daratumumab was 11% across Study MMY2002 and Study GEN501. Following treatment with daratumumab, 3 stringent complete responses (sCRs), 2 complete responses (CRs), and 12 VGPRs were observed across both studies. The CR/sCR rate was 3%.

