11.4. Pharmacokinetic Analyses

Pharmacokinetic analyses will be performed on the PK-evaluable population, defined as subjects who have received at least 1 dose of daratumumab or atezolizumab and have at least 1 postinfusion sample.

All concentrations below the lowest quantifiable concentration or missing data will be labeled as such in the concentration database. Concentrations below the lowest quantifiable concentration will be treated as zero in the summary statistics. The number of subjects and samples excluded from the analysis will be clearly documented.

Descriptive statistics will be used to summarize daratumumab and atezolizumab serum concentrations at each sampling time point. C_{\min} is defined as the minimal concentration observed immediately before infusion and C_{\max} is defined as the maximum concentration observed at the end of infusion, as presented in the summary of serum concentration by sampling time point and route of administration. Other PK parameters, if available, may also be summarized.

If sufficient data are available, population-PK analysis of serum concentration-time data of daratumumab or atezolizumab may be performed and may be combined with data from other studies. If the population-PK analysis is conducted, details will be given in a population-PK analysis plan and the results of the analysis will be presented in a separate report.

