2.5. Imputation of Missing Data

Data imputation will be limited and detailed rules will be specified in DPS.

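### SAP 7.1 sets unquantifiable concentrations to zero and also reports a geometric mean, which is then zero or undefined wherever such a value occurs

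*SAP*

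**What the plan says.** SAP 7.1 (Pharmacokinetics) gives one rule for BLQ concentrations: "Concentrations below the lowest quantifiable concentration will be treated as zero in the summary statistics". The rule is not limited to particular statistics. BLQ values must also be labelled as such in the data presentation.

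The section then says that descriptive statistics, with number of observations, mean, standard deviation, median and range as examples, "will be used to summarize daratumumab and atezolizumab serum concentrations at each sampling time point". It goes on to say that "coefficient variation and geometric mean will be provided in the pharmacokinetic concentration summary". It does not say whether the coefficient of variation is arithmetic or geometric.

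Protocol 11.4 has the same zero rule but names no geometric mean. It describes Cmin as "defined as the minimal concentration observed immediately before infusion", so predose samples belong in these tables. SAP 2.5 says of missing data in general: "Data imputation will be limited and detailed rules will be specified in DPS". The DPS (data presentation specifications) is not among the documents.

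**The concern.** A geometric mean is defined only for positive values. If a zero is put in wherever the assay cannot quantify the drug, the geometric mean at that time point stops describing the sample, however many other values are well quantified. Whoever programs the table must then either print 0 or a missing result, or depart from the SAP by a rule that nobody has written down.

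Serum Cmin and Cmax of both drugs are secondary endpoints (Protocol 2.1.2), so the affected statistic belongs to a named endpoint. At stake is a reported figure that is meaningless as specified, or one whose meaning depends on an unrecorded choice.

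**Working it through.** The documents give no figure to reproduce. The check is algebraic, with a numerical illustration.

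**Formula.** For n concentrations x, GM = (x₁ × x₂ × … × xₙ)^(1/n) = exp(mean of log x). If any x = 0, the product form gives 0. The log form needs log(0), which does not exist.

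**Inputs from the documents.**
- The zero rule and the geometric mean: both in SAP 7.1, both applied by time point.
- A scale for illustration: Protocol 1.3.1 reports, for the myeloma schedule, "The mean predose (trough) serum concentration at the end of weekly dosing was 573" µg/mL.

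**Assumptions.** n = 45 (half of the 90 planned), and the assay limit (LLOQ), which the documents do not give.

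**Simple case: 44 values at 573 and one BLQ value.**
- Arithmetic mean with the zero: 44 × 573 / 45 = 560.3.
- SD with the zero: 573 / √45 = 85.4. Arithmetic CV: 85.4 / 560.3 = 15.2%.
- Median: 573.
- Geometric mean with the zero: 0, or undefined.
- Geometric mean of the quantifiable values only: 573, on n = 44.
- Geometric mean with LLOQ/2 substituted, exp[(44 × ln 573 + ln(LLOQ/2)) / 45]: 458, 473 or 490 for an LLOQ of 0.05, 0.2 or 1 µg/mL. Against 573 that is a fall of between (573 − 490)/573 = 14% and (573 − 458)/573 = 20%.

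**With spread.** Values were simulated as log-normal with median 573 and log-SD 0.4 (both the shape and the SD are assumptions). Each row is a fresh draw, so compare within rows.

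| BLQ of 45 | Arithmetic mean | Median | GM under the SAP rule | GM, quantifiable only |
|---|---|---|---|---|
| 0 | 596 | 575 | 558 | 558 |
| 1 | 571 | 581 | 0 or undefined | 558 (n = 44) |
| 5 | 529 | 534 | 0 or undefined | 547 (n = 40) |
| 45 | 0 | 0 | 0 or undefined | none |

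Two details follow. With 5 BLQ values, the quantifiable-only geometric mean (547) exceeds the arithmetic mean beside it (529). That cannot happen when both use the same positive values, and it shows why the geometric mean needs its own n. With all 45 BLQ, the arithmetic CV is 0/0.

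**Where BLQ values arise.** A drug-naive subject has no drug in serum before the first dose. The summary of changes for Amendment 2, used here only as evidence that the sample was scheduled, says "Cycle 1 Day 1 predose pharmacokinetic sample for atezolizumab will be for all arms". Elsewhere BLQ values are possible but not shown. Protocol 9.5.1 asks subjects who stop treatment to return for immunogenicity evaluation during follow-up, and 9.5.2 has every antibody sample assayed for concentration too. The crossover predose atezolizumab sample is not drug-naive: Protocol 4.3.1 puts that dose 21 to 42 days after the last one.

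**The case against.** The strongest reply is that little depends on this. The one time point sure to be affected is the first predose sample, where nearly every value should be BLQ and a geometric mean of 0 misleads nobody. On treatment, the documents point towards quantifiable troughs. Protocol 1.3.1 reports the 573 µg/mL mean daratumumab trough, a half-life of about 18 days, and no anti-daratumumab antibodies in 199 evaluable subjects. Protocol 3.4 expects the atezolizumab regimen to hold troughs at or above 6 µg/mL. The statistics that SAP 7.1 lists first, and its plots of mean and SD, all tolerate zeros. This stands, and it limits the size of the point. It is not proof that on-treatment BLQ values are absent: the figures come from other populations or projections, and the LLOQ is unknown.

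A second reply is that the DPS may hold the missing rule. That does not settle the matter, because SAP 7.1 already gives an explicit rule without exception and a different one in the DPS would contradict it. Nor does the end of sampling (Protocol 9.5), since samples already taken can still be summarised.

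A reader might infer more than the documents support:
- **Low troughs reported with an upward bias because software drops zeros.** Neither document names software or describes such handling, and no on-treatment time point with BLQ values is shown.
- **A failing geometric CV.** The SAP names only a coefficient of variation. The arithmetic version works with zeros unless every value is zero.
- **The same conflict in Protocol 11.4.** That section plans no geometric mean, so its zero rule conflicts with nothing there.

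**Conclusion.** The point holds, and it is minor. As written, SAP 7.1 yields a geometric mean of 0 or undefined at every time point with one or more BLQ values. This needs no distributional assumption. It is a stated rule giving an unusable result, not merely a missing detail.

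The reach is one added statistic in descriptive pharmacokinetic tables. It covers the drug-naive predose sample and, depending on an unknown BLQ fraction, perhaps follow-up or low-exposure samples. Time points without BLQ values are unaffected. The documents do not support saying that the Cmin endpoint as a whole is compromised. The 14% to 20% range above rests on an assumed n and LLOQ, and on the other values being equal. It shows only that the choice of rule changes the number and so should be fixed in advance.

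**What to change.** In SAP 7.1:
- Limit the zero rule to the arithmetic statistics, median and range.
- Exempt the geometric mean by one prespecified rule. Two workable options are to compute it on quantifiable values only and print its own n, or to report it as not calculated when any BLQ value is present. LLOQ/2 is a possible alternative, but its result depends heavily on the assay limit, as shown above, so it is not an obvious default.
- Show the number of BLQ values at each time point.
- State that the coefficient of variation is arithmetic, and not calculated when all values are BLQ.

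The cost is a short addition to the text and one more row or column in the table shell. No new data are needed. The downside is that at affected time points the geometric mean will be absent or will rest on a smaller, labelled n.
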